6.1. Primary Analysis of Efficacy

All subjects who received at least one dose of study medication, will be used as the primary population for assessment of efficacy. The proportion of people whose NP sample becomes positive at least once during the trial will be compared between the study groups using Chi square or Fisher exact test. Survival analysis will be utilized to estimate the potential effects of hydroxychloroquine on COVID-19 free survival times. We will apply generalized linear mixed models to compare the positive conversion rate of COVID-19 between the study arms while controlling for other confounding factors. AIC and BIC criteria will be used to choose an appropriate covariance structure between the measurements collected at consecutive visits. An interaction effect between time and study group will be added to the model to evaluate whether the relative risk of a positive conversion changes from visit to visit.

7. Missing data

If the proportions of missing data are above 5%, multiple imputation methods will be used to construct complete data sets under different missing patterns. Otherwise, linear mixed models will be used that allow for presence of missing values in the data.

8. References

- ¹ Bedford J, Enria D, Giesecke J, Heymann DL, Ihekweazu C, Kobinger G, Lane HC, Memish Z, Oh MD, Sall AA, Schuchat A, Ungchusak K, Wieler LH; WHO Strategic and Technical Advisory Group for Infectious Hazards. COVID-19: towards controlling of a pandemic. *Lancet*. 2020 Mar 17. pii: S0140-6736(20)30673-5. doi:10.1016/S0140-6736(20)30673-5. [Epub ahead of print] PubMed PMID: 32197103
- ² Zhou D, Dai SM, Tong Q. COVID-19: a recommendation to examine the effect of hydroxychloroquine in preventing infection and progression. *J Antimicrob Chemother*. 2020 Mar 20. pii: dkaa114. doi: 10.1093/jac/dkaa114. [Epub ahead of print] PubMed PMID: 32196083.
- ³ Sahraei Z, Shabani M, Shokouhi S, Saffaei A. Aminoquinolines Against Coronavirus Disease 2019 (COVID-19): Chloroquine or Hydroxychloroquine. *Int J Antimicrob Agents*. 2020 Mar 16:105945. doi: 10.1016/j.ijantimicag.2020.105945. [Epub ahead of print] PubMed PMID: 32194152.
- ⁴ Devaux CA, Rolain JM, Colson P, Raoult D. New insights on the antiviral effects of chloroquine against coronavirus: what to expect for COVID-19? *Int J Antimicrob Agents*. 2020 Mar 11:105938. doi: 10.1016/j.ijantimicag.2020.105938. [Epub ahead of print] PubMed PMID: 32171740.

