This prospective open label trial will study the safety, tolerability, and efficacy of hydroxychloroquine 400 mg po in qualified health care workers.

Qualified individuals will be prescribed oral hydroxychloroquine 400 mg twice a day (two 200 mg tablets twice a day) on day 1 followed by two 200 mg tablets once a week for a total of 7 weeks. Dose de-escalation is permitted during the study if indicated clinically. Please refer to [Section 7.3.1](#) for additional details on dose escalation and dose de-escalation.

All study individuals will follow the same visit and assessment schedule. Following study recruitment, participants will be scheduled to be assessed in person during treatment at days 7, 14, 21, 28, 35, 42 and 49.

Healthcare workers who are qualified for the trial but decline participation in receiving the treatment will form the control group and will be offered an observational registry where the same NP COVID-19 sampling schedule and other assessments will be followed with the exception of blood testing. The clinical outcomes will be captured in the same manner and with the same definitions as the clinical arm.

Number of Subjects (planned):

360 individuals will be enrolled into the study with half enrolling in the active treatment study and the other half, those who refuse to get the study treatment, will be entering an observational registry considered as the control group.

Main criteria for inclusion:

1. Adult male and female healthcare workers ≥ 18 to ≤ 75 years of age upon study consent
2. Healthcare workers with
 - One day or more of exposure to suspected and/or positive COVID-19 patients, including but not limited to those working in the Emergency Department or Intensive Care Unit.OR
 - Unprotected exposure to a known positive COVID-19 patient within 72 hours of screening.
3. Afebrile with no constitutional symptoms
4. Willing and able to comply with scheduled visits, treatment plan, and other study procedures
5. Evidence of a personally signed and dated informed consent document indicating that the subject (or a legally acceptable representative) has been informed of all pertinent aspects of the study prior to initiation of any subject-mandated procedures

Major exclusion criteria:

1. Participation in other investigational clinical trials for the treatment or prevention of SARS-COV-2 infection within 30days

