The power calculation, which was based on Pearson Chi Square test, assumes the following:

- One-sided Type I error rate of 0.05
- Anticipated positive NP samples rate of 30% in the clinical arm
- A 40% lower risk of a positive NP sample comparing the hydroxychloroquine group vs the controls
- Loss to follow-up rate of 15%

Primary analysis of efficacy:

The proportion of individuals who tested positive at least once during the study period will be compared between the clinical and the control arms. In addition, the potential effect of hydroxychloroquine on COVID-19 free survival time will also be explored by utilizing appropriate statistical methods. An intent-to-treat approach will be used throughout the analysis with the control group as the referent. A p-value < 0.05 will be considered statistically significant and a risk reduction of 5% will be considered as of smallest clinical importance.

Study Rationale

It is clear that close interaction of health care workers with patients put them at higher risk of getting exposed to infectious diseases. Failing to provide a safe environment for health care workers could cripple the medical system especially during an Epidemic outbreak like COVID-19. It is imperative to make sure that doctors and nurses do not get sick in high numbers; not only because that will contribute to spreading the virus among vulnerable patients but also due to their subsequent role in reducing the number of responding personnel. As a result, it is of utmost importance to provide effective prophylaxis to healthcare workers who are exposed to COVID-19.

Schema for Study of Prophylactic Therapies for COVID-19 Exposure

The trial design is initially for a 7 week treatment period which can be divided into 7 bins of time to allow a flexible design. Given the fluid nature of information flow in this pandemic that for example, new information comes forward clearly showing that 6 days is a sufficient period of time for proven prophylaxis, this trial design can be altered. Conversely if each subsequent qualifying exposure calls for another 6-day bin of time, the protocol can flex to the maximum 7 week period as stated for resource planning.

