Once subject's eligibility is approved they may choose to either receive hydroxychloroquine or enter the observational registry. In both cases subjects will be tested for COVID-19 positive conversions on weekly nasopharyngeal (NP) sampling. The swab samples will be collected by trained personnel. Nasopharyngeal swab will be collected in a VCM medium tube or equivalent (UTM) or E-swabs/Amies medium (minitip-NP swab) or M4, M4RT, M5 and M6 transport media. The Roche Cobas test will be utilized for detecting nucleic acids from SARS-CoV-2 in nasopharyngeal swab samples collected from study participants.

The safety of the study participants will be ensured by closely monitoring the (serious) adverse events occurring during the trial. In addition, we will comply with the standard of care for regular prescribing of hydroxychloroquine which does not require a routine assessment of subject's health status especially for short-term use. However, since the package insert for hydroxychloroquine cautions on using antimalarial

compounds for individuals with hepatic disease, alcoholism, G-6-PD and severe blood disorder we will not include individuals having those diseases in our study.

Subjects who choose to enter the clinical arm of the study will receive hydroxychloroquine for a total of 7 weeks. The study drug supply will be maintained either through Baylor Scott & White pharmacies or directly from a manufacturer.

The logistics of drug dispensing will be specified based on the availability of drug supplies and also the mechanism through which the drug would be accessed. If there is enough supply of hydroxychloroquine we will dispense the drug as feasible in advance for future visits, otherwise a weekly supply would be provided to participants at each visit.

At the end of the study, after the last subject visit is completed. All collected data will be analyzed with the study population being those who either received hydroxychloroquine or entered the observational registry.

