7.3. Treatment Assignment

Qualified individuals may choose which group they want to be in. Subjects in the treatment group will receive hydroxychloroquine for 7 weeks. Those who decide to opt out of receiving treatments will compose the control group.

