5.1. Intention-to-treat (ITT)

- All subjects who received the study drug
- All subjects who participated in at least one post-baseline assessment

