5.2. Per Protocol (PP)

All randomised study subjects completing the whole study period (complete cases)

6. Analyses

All statistical analyses and data summaries will be performed using SAS® (Version 9.1 or higher) or other validated software. The SAP will serve as the final arbiter of all statistical analyses. Data will be summarized overall using descriptive statistics. Continuous data will be summarized with number of subjects (n), mean, median, minimum, maximum, relevant quartiles, standard deviation, coefficient of variation, and geometric mean (where applicable). Categorical data will be summarized using frequency counts and percentages. Chi Square or Fisher exact test will be used for comparing binary outcomes between treatment and control groups. Continuous variables will be compared between the study groups by means of two sample T test or Wilcoxon-rank-sum test.

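### The primary efficacy population requires at least one dose, which no control receives, and the plan's other statements of the set disagree on who is in it

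*SAP*

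**What the plan says.** SAP 6.1 and Protocol 12.2.1 use the same sentence: "All subjects who received at least one dose of study medication, will be used as the primary population for assessment of efficacy". The sentence after it, in both places, compares the proportion ever NP-positive between the study groups by chi-square or Fisher exact test.

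The control group is defined by not taking the drug. The synopsis, under the planned number of subjects, says that "those who refuse to get the study treatment, will be entering an observational registry considered as the control group". Protocol 7.3 says "Those who decide to opt out of receiving treatments will compose the control group".

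Three other statements bear on who is analysed:

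- Synopsis, primary analysis of efficacy: "An intent-to-treat approach will be used throughout the analysis with the control group as the referent".
- Synopsis, end of the schema text: "All collected data will be analyzed with the study population being those who either received hydroxychloroquine or entered the observational registry".
- SAP 5.1, under the intention-to-treat heading, gives two bullets with no connecting word: "All subjects who received the study drug" and "All subjects who participated in at least one post-baseline assessment". SAP 6.1 does not refer to this set.

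On precedence, SAP section 6 states: "The SAP will serve as the final arbiter of all statistical analyses". Protocol 12.2 says the same.

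**The concern.** A rule based on receiving study drug suits a trial in which every arm takes something. Here one arm takes nothing by design, so the rule and the comparison that follows it cannot both be carried out. The sentence is wrong as written; it is not merely short of detail.

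Once it is set aside, the analyst needs another rule, and the plan's remaining statements give different answers for three kinds of participant: people who chose hydroxychloroquine but never took it, treated people with no follow-up, and registry members with no follow-up. Participants choose their own group and the trial is open label, so the rule for entering the primary set should be the same in both groups and should be fixed before analysis.

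**Working it through.** **Inputs.** Planned total 360, half in each group (synopsis and SAP 2.1): 360 / 2 = 180 treated and 180 controls. Controls take no study drug (synopsis, Protocol 7.3). Day 1 is the first-dose day (Protocol Table 3, footnote b). NP samples are scheduled on Day 1 and at each weekly visit (Protocol Table 3).

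**Step 1: the dose rule applied literally.** Treated: up to 180 of 180. Controls: 0 of 180. The two-group table has an empty column, so neither test can be computed.

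**Step 2: each statement set out by type of participant.** HCQ means that the person chose hydroxychloroquine. Follow-up means at least one post-baseline assessment. Intent-to-treat in the synopsis is taken in its usual sense, since the synopsis does not define it.

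| Participant | SAP 6.1 / Protocol 12.2.1 | SAP 5.1, both bullets | SAP 5.1, either bullet | Synopsis, study population | Synopsis, intent-to-treat |
|---|---|---|---|---|---|
| HCQ, dosed, follow-up | in | in | in | in | in |
| HCQ, dosed, no follow-up | in | out | in | in | in |
| HCQ, never dosed, follow-up | out | out | in | out | in |
| HCQ, never dosed, no follow-up | out | out | out | out | in |
| Registry, follow-up | out | out | in | in | in |
| Registry, no follow-up | out | out | out | in | in |

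No two columns are identical. The first two admit no controls. The last three admit controls but differ from one another.

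**Step 3: which differences can change the primary test.**

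- *No follow-up.* Under the either-bullet reading, a dosed person with no follow-up stays and a registry member with no follow-up goes. Neither has a post-baseline NP result, so a chi-square or Fisher test on observed post-baseline outcomes is the same whichever set is used. The unequal entry condition acts only if missing outcomes are imputed.
- *Never dosed, with follow-up.* These people do have NP results, so including or dropping them can change the observed comparison. The documents give no number. If 0% to 5% of the 180 who choose the drug never take it (an assumption), that is 0 to 0.05 × 180 = 9 people. The synopsis study population would then be 360 − 9 = 351 to 360, against 360 under intent-to-treat. The true figure is probably small, because dosing starts on Day 1.

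**Step 4: does precedence settle it?** No. The dose rule and the two-bullet set are both in the SAP. The two clearest statements that include controls are in the protocol synopsis, which yields to the SAP.

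**Step 5: baseline positives.** The endpoint is conversion to positive. Swabbing starts on Day 1, and Protocol 8.1 and 8.2 do not require a negative test at entry. None of the five definitions says what happens to someone already positive on Day 1, so a corrected definition has to.

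**The case against.** The strongest reply is that nobody would be misled. The between-group test, the intent-to-treat statement with controls as referent, and the synopsis description of the study population all show that controls belong in the analysis. Both bullets of SAP 5.1 begin in the same way and read naturally as a union, and the both-bullets reading would empty the control arm, which SAP sections 6 and 6.1 rule out. Protocol 12.2 also requires the SAP before database lock.

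Most of this stands. A reader might infer that the trial would analyse treated people only; the documents do not support that. A reader might also infer that the SAP contains no rule that could be used. That too goes too far: SAP 5.1 read as a union does admit controls.

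The reply does not remove the contradiction. The sentence that names the primary population still excludes every control, SAP 6.1 does not point to SAP 5.1, and the union reading sets a different entry condition for each group. Having a SAP before lock does not help if that SAP carries the conflict.

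**Conclusion.** The point holds as an error of definition that should be corrected before analysis. Its certain size is that 0 of 180 planned controls satisfy the stated primary population. In practice the remaining ambiguity is likely to be small: 0 to 9 people who chose the drug and never took it, under the assumed 0% to 5%, plus an unequal follow-up condition that matters only under imputation.

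It is tempting to read this as a source of bias in a known direction, or as a loss of power from dropped controls. The documents support neither. Nothing in them says which way the never-dosed or the early losses would differ. People with no post-baseline result add nothing to an observed-data test in either group, so their place in the set does not change its power.

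The conclusion assumes that registry members take no study drug, as the design states, and that the ever-positive outcome is counted from swabs after Day 1. If a Day 1 positive counted as an event, a registry member positive on Day 1 with no follow-up would also be treated differently under the competing sets.

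**What to change.** 1. In SAP 6.1, replace the sentence with: 'The primary efficacy population is all eligible participants enrolled in either group (hydroxychloroquine or registry), analysed by the group chosen at enrolment.'
2. Make SAP 5.1 state that same single rule in place of its two bullets, and cite it in 6.1.
3. State, identically for both groups, how participants with no post-baseline NP result are handled and how those already NP-positive on Day 1 are handled.
4. Minor: SAP 5.2 defines the per-protocol set by randomised subjects, but nobody is randomised and no analysis uses the set. Replace the word with 'enrolled' or delete the set.

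The cost is wording only, with no new data or participants. Because the SAP is the final arbiter, correcting it is enough to settle the analysis. Protocol 12.2.1 can be aligned at the next amendment, since a separate one would need the notification and approval steps in Protocol 15.5.

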18 APPENDICES

18.1 Appendix I: Registry for Screened and Not Randomized

For healthcare workers who have been screened and who would have qualified as eligible subjects but decline participation because of personal choice or logistical reasons, a registry will be offered with the same baseline data collection, schedule of NP sampling, and capture of outcomes. This will serve as a form of community surveillance for the medical center and will have a sample size that will not be pre-specified and limited only by the availability of NP COVID-19 sampling. For those who develop a positive NP test, the current guidance from the medical center administration and in concert with guidance from the U.S Federal Government, State and Local Authorities, Centers for Disease Control, and State and Local Health Departments, will all be applied in terms of next steps in monitoring and control of COVID-19 viral spread.

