2.1. Sample size calculation

A total sample of 360 individuals (180 in each arm) would provide at least 80% power to detect a relative risk reduction of 40% in the rate of positive NP samples when the anticipated rate of positive conversion among those taking hydroxychloroquine is approximately 30%.

The power calculation, which was based on Pearson Chi Square test, assumes the following:

- One-sided Type I error rate of 0.05
- Anticipated positive NP samples rate of 30% in the clinical arm
- A 40% lower risk of a positive NP sample comparing the hydroxychloroquine group vs the controls
- Loss to follow-up rate of 15%

3. Aims and objectives

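### Groups are self-selected, but the planned confounder-adjusted model is not ranked above the crude chi-square/Fisher test and its confounders are not listed

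*SAP*

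**What the plan says.** **Assignment.** Protocol 7.3: "Qualified individuals may choose which group they want to be in". Those who opt out of the drug are the controls. Appendix I describes the registry as being for eligible workers who "decline participation because of personal choice or logistical reasons".

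**Synopsis, on the primary efficacy analysis.** "The proportion of individuals who tested positive at least once during the study period will be compared between the clinical and the control arms". COVID-free survival will be explored as well. The same paragraph says "A p-value < 0.05 will be considered statistically significant", without naming a test. It does not mention adjustment.

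**Protocol 12.2.1 and SAP 6.1 (same text).** Three analyses appear in this order:
1. The proportion positive at least once "will be compared between the study groups using Chi square or Fisher exact test".
2. Survival analysis of COVID-free time.
3. A generalized linear mixed model of conversion that adjusts for confounders, with AIC/BIC used to choose the covariance structure and a time-by-group interaction added.

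The three are not ranked, and no confounder or rule for selecting covariates is given.

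**Sample size (Protocol 12.1, SAP 2.1).** "The power calculation, which was based on Pearson Chi Square test", with one-sided alpha 0.05, 30% positive in the clinical arm, a 40% lower risk on drug and 15% loss.

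SAP section 6 gives the SAP the last word on all analyses, so no later document is promised to settle the order.

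**The concern.** Nothing in the design balances takers and refusers. Workers who see themselves as more exposed may seek the drug. Others may decline because of rota or access, and those reasons can also track exposure. A crude difference in proportions then mixes the drug effect with the difference between the kinds of people who chose each group. It can show benefit or harm that the drug did not cause, or hide a real effect. The direction cannot be known in advance.

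The plan recognises this by including an adjusted model, but leaves two decisions open: which of the analyses answers the primary objective, and what the model adjusts for. If the crude and adjusted results fall on different sides of the significance threshold, either could be presented as primary. Covariates could also be settled after the outcomes are known.

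**Working it through.** **1. The plan's own figure.** With p̄ the mean of the two rates, n per group = [z_α√(2p̄(1−p̄)) + z_β√(p₁(1−p₁)+p₂(1−p₂))]² / (p₁−p₂)², with z_α = 1.645 and z_β = 0.842.
- As written (30% on drug, so 0.30/0.60 = 50% in controls): (1.140 + 0.571)²/0.20² → 74 per group; 74/0.85 → 88, or 176 in total. This does not give 360.
- Reading 30% as the control rate (18% on drug): (0.994 + 0.503)²/0.12² → 156 per group; 156 × 1.15 → 180, or 360 in total.

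Either way this is an unadjusted two-proportion formula with no allowance for adjustment. Evaluable number: 180 × 0.85 = 153 per group. Power = Φ[(|p₁−p₂| − z·s₀)/s₁], where s₀ = √(2p̄(1−p̄)/n) and s₁ = √([p₁(1−p₁)+p₂(1−p₂)]/n). At n = 153, one-sided, this is 79.4% for 18% vs 30% and 97.5% for 30% vs 50%.

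**2. Error of the crude test when the drug does nothing.** The documents give no imbalance, no exposure risk ratio and no overall rate, so these are assumptions: one binary high-exposure factor with risk ratio k = 2 or 3, 30% overall conversion, 153 per group. With e_t and e_c the shares highly exposed among takers and refusers:
- r₀ = 0.30/[1+(k−1)(e_t+e_c)/2]
- risk in a group = r₀[1+(k−1)e]

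Example, k = 2, 30% vs 50%: r₀ = 0.30/1.4 = 0.2143; takers 0.2143 × 1.3 = 27.9%; refusers 0.2143 × 1.5 = 32.1%. That is a spurious 4.3-point difference and a crude risk ratio of 0.87.

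Simulated rejection rates (200,000 trials per setting, Pearson z without continuity correction; ranges are k = 2 to k = 3):

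| Takers vs refusers highly exposed | Crude, two-sided 0.05 | Crude, one-sided 0.05 toward benefit | Crude and stratified tests disagree, two-sided |
|---|---|---|---|
| 45% vs 50% | 5.5-6.1% | 7.4-8.9% | 2.9-4.5% |
| 40% vs 50% | 6.9-9.3% | 10.5-14.9% | 5.0-8.4% |
| 30% vs 50% | 13-25% | 21-36% | 13-25% |

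A Mantel-Haenszel test stratified on true exposure stays at about 5% throughout.

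**3. Opposite imbalance, real effect.** Takers 50% and refusers 30% highly exposed, true risk ratio 0.60. With a 30% no-drug rate and k = 2: takers 0.2143 × 1.5 × 0.6 = 19.3%, refusers 0.2143 × 1.3 = 27.9%, crude risk ratio 0.69.
- No-drug rate 30%: crude two-sided power falls from about 70% to 42% (k = 2) or 28% (k = 3). The stratified test keeps 69-71%.
- No-drug rate 50%: crude two-sided power falls from about 95% to 74% or 52%.

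**4. Against the plan's own threshold.** The synopsis says "a risk reduction of 5% will be considered as of smallest clinical importance". If this is relative, confounding alone gives a crude risk ratio of 0.95 when [1+(k−1)e_t]/[1+(k−1)0.5] = 0.95, that is, e_t = 42.5% (k = 2) or 45% (k = 3) against 50%. If it means percentage points, at 30% overall it takes about 27% or 35% against 50%.

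**The case against.** The strongest reply is that adjustment is already planned. The mixed model stands under the primary-analysis heading in both documents, and its wording echoes the primary endpoint. That is correct. A reader might infer that the plan ignores confounding, and the documents do not support that. What is missing is a rank and a covariate list.

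Three other inferences also go too far:
- **That the p<0.05 rule belongs to the crude test.** The sentence follows one on survival and one on intention-to-treat for the whole analysis. It is a general rule, tied to neither test.
- **That using chi-square for power makes it the primary test.** By itself it does not. It shows only that the sample size makes no allowance for adjustment.
- **That the mixed model can give only visit-specific effects.** The stated purpose of the interaction is to see whether the relative risk varies over visits. Nothing says that the interaction model supplies the treatment estimate.

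On size, the inputs are assumed and mild imbalance barely moves the error. Everyone enrolled has met an exposure criterion, which may narrow the contrast. But that criterion runs from one day around suspected cases to unprotected contact with a known case, so room for imbalance remains. Equal groups of 153 are also uncertain, because Appendix I says the registry size is not set in advance while the sample size section assumes 180 per arm.

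These points limit how far the simulations can be pressed. They do not answer which result decides.

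**Conclusion.** The concern holds as under-specification of the primary analysis in a self-selected comparison. The unadjusted comparison of proportions is the first-listed test, the only definite comparison in the synopsis primary analysis, and the basis of the power. The adjusted model is neither placed above it nor given covariates.

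The need to fix this follows from the design, since participants pick their group. It does not depend on any particular simulated figure. The possible distortion ranges from negligible to large on the stated assumptions, in either direction. Step 3 depends heavily on the no-drug rate, so the 28-42% power figure should not be quoted without its 52-74% counterpart.

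Adjustment reduces the problem and does not remove it. In simulation, with exposure recorded at 80% sensitivity and specificity, the stratified test's two-sided error was 5.7-6.7% (40 vs 50) and 8.5-13.6% (30 vs 50).

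The sidedness of the test and the at-least-one-dose wording of the primary population are separate matters and carry no weight here.

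**What to change.** In the synopsis, Protocol 12.2.1 and SAP 6.1, before outcomes are examined:
- Name one baseline-confounder-adjusted comparison of ever-positive NP status by Day 49 as primary, reporting an adjusted risk ratio and risk difference. Standardised logistic regression or overlap weighting would do.
- Report the crude chi-square/Fisher result as descriptive.
- Keep the survival analysis and mixed model as supportive, with the interaction as a secondary test. A model of repeated visit results does not directly give the cumulative risk by Day 49.
- List the covariates, from screening or Day 1 only: qualifying exposure type, shifts and hours in COVID units, aerosol procedures, close contact, PPE adequacy, work area (ED/ICU/other), age, sex and calendar week of enrolment. Keep later exposure reports out of the primary model.
- State that the chi-square power does not allow for adjustment. Add one sensitivity analysis for unmeasured confounding, and say that unmeasured or mismeasured confounding limits the conclusion.

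**Cost.** Wording changes and modest analysis work. Most of the data are already planned: Appendix I says "a registry will be offered with the same baseline data collection, schedule of NP sampling, and capture of outcomes", and the exposure questionnaire is scheduled at screening and Day 1. Work area is needed anyway for the ED-versus-ICU objective.

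The price is precision. Simulations with 306 analysed and 10 covariates, run without confounding, gave adjusted-to-crude standard-error ratios of 0.98-1.04 when covariates barely separate the groups (c-statistic 0.60), rising to 1.09-1.16 at 0.77. Multiplying s₀ and s₁ in the power formula by 1.04 and 1.16 (153 per group, one-sided 0.05) gives:
- 18% vs 30%: from 79.4% to 76.6% and 68.4%.
- 30% vs 50%: from 97.5% to 96.6% and 92.8%.
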